Clinical interview. Trained clinical interviewers will conduct the CAPS-5 interview to establish PTSD diagnosis and SCID-5 interview to establish insomnia diagnosis. This will take place over phone or video. The SCID-5 will also be used to rule out diagnostic exclusion criteria and establish comorbid mental health conditions for data analytic purposes. A brief medication interview will be conducted to obtain information about recent and current medication use. Interviews will be audio-recorded and reviewed by the Stress and Health Research Program's clinical assessment supervisor \*This is solely for research purposes.

Baseline prospective sleep data. Once eligibility is established, the Veteran will be shown how to complete a sleep diary. He or she will then record one week of baseline sleep data. Research staff will email the Veteran a link to enter sleep diary data via Qualtrics. The Veteran's PAP setup appointment (if needed) and treatment schedule will be planned. \*This is for research purposes; however, please note that completing a sleep diary is also part of routine care.

**Actigraphy.** The actigraph is a device worn on the risk to measure time asleep vs. awake. A subset of participants will be asked to wear the actigraph. The information will be used solely for research purposes. It is not part of the treatment.

**Baseline appointment**. The Veteran will complete pre-treatment measures. He or she will be randomized to either AIR or SE. \* Many of the pre-treatment measures are completed as part of routine care, but some are added for research purposes.

**Randomization procedure.** A block-randomization procedure will be used to assign participants to AIR or SE in a 1:1 ratio. Block sizes will be a random permutation of 4 and 6. Statistical consultant [REDACTED] will produce the computer-generated list. Each therapist will have his or her own randomization list. The randomization to treatment is for research purposes.

**Weekly assessment.** At the start of each treatment appointment, the Veteran will complete two self-report questionnaires assessing sleep (ISI and ESS). The Veteran's PAP adherence data and actigraphy data will also be downloaded or requested verbally. A copy of the Veteran's sleep diary will be obtained. At his or her final treatment appointment, the Veteran will be asked to complete a sleep diary to submit at the Post-Treatment

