outliers will be conducted to evaluate influence on outcomes. Primary analyses will be unadjusted intent-to-treat analyses, with all subjects randomized to a treatment condition included. We will use linear mixed models, which are robust to data missing at random, to accommodate missing data due to dropout. Demographic and other baseline variables that show large group imbalances despite randomization will likewise be entered as covariates in a secondary sensitivity analysis, but will not be included in the primary analyses. Substantial differences in inferences supported by the primary and secondary analyses would indicate a potential problem of randomization failure, and would warrant caution in interpreting results of the primary analyses

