## Hypothesis Testing.

**Hypothesis 1a**: Veterans receiving AIR will demonstrate improved quality of life (WHOQOL-BREF; primary outcome) and functioning (FOSQ-10; secondary outcome) compared with control at post-treatment and follow-up assessments.

Analyses. The WHOQOL-BREF psychological domain score will be considered the primary outcome of the study, whereas the FOSQ-10 is a secondary measure of functioning. Both the WHOQOL-BREF and FOSQ-10 are administered at pre-treatment, week 3, week 5, post-treatment, and 3-month follow-up. Separate analyses will be conducted for each measure. A linear mixed model will be estimated for each score with subjects entered as a random effect and treatment group and time entered as fixed effects. Pre-treatment scores will be entered as a covariate, and time (week 3, week 5, post-treatment, and follow-up) will be entered as a categorical predictor to accommodate non-linear changes over time. The hypothesis will be tested by the significance of the group differences in baseline-adjusted post-treatment scores. The baseline-adjusted group difference at post-treatment will be divided by the standard deviation of baseline scores to calculate the standardized effect size. Durability of effects at 3 months will be tested by examining group differences in baseline-adjusted follow-up scores.

**Hypothesis 1b**: Veterans receiving AIR will demonstrate greater reduction in symptoms of insomnia (ISI and actigraphy) and PTSD (CAPS), and greater adherence to PAP (device data capture) compared with control at post-treatment and follow-up assessment.

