Analyses for insomnia: The ISI is administered several times over the course of treatment: pre-treatment, sessions 1-6, and post-treatment. A linear mixed model will be estimated for each score with subjects entered as a random effect and treatment group entered as a fixed effect. Pre-treatment score will be entered as a covariate. Time (sessions 1-6 and post-treatment) will be modeled linearly and non-linearly, with the choice of functional form governed by likelihood ratio tests and BIC criteria. The choice of whether to include a random effect for time will be determined by choosing the best fitting model according to the likelihood ratio test. All modeling choices will be made before examining any significance tests. The hypothesis will be tested by the significance of the group difference in baseline-adjusted marginal means (least squares means) at post-treatment derived from the full model. The difference in marginal means at post-treatment will be divided by the pre-treatment standard deviation to calculate the standardized effect size. These analyses will be repeated with the insomnia variables of interest derived from actigraphy

(TST and WASO), with data grouped by week. The primary variable for this analysis will be TST.

**Analyses for PTSD:** The CAPS is administered at pre- and post-treatment. The primary analysis examining the CAPS will be based on the CAPS total score. A linear mixed model will be estimated for CAPS total score with subjects entered as a random effect and treatment group and time point entered as fixed effects. The hypothesis will be tested by the significance of the group by time interaction. The baseline-adjusted group difference at post-treatment will be used to calculate the effect size.

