Analyses for PAP adherence: PAP adherence will be measured via device data capture. The primary metric used to measure this will be average hours of PAP use in the past 7 days. This will be measured starting at session 1 and will continue through post-treatment, and again for 1 week at follow-up. A linear mixed model as described above for the ISI will be estimated for PAP adherence. The hypothesis will be tested by the significance of the group difference in marginal means at post-treatment derived from the full model. The difference in marginal means at post-treatment will be divided by the pre-treatment standard deviation to calculate the standardized effect size. Durability of effects at 3 months will be tested by comparing model-adjusted marginal effects for the two groups at follow-up. Effect size of treatment at 3 months will be calculated from the marginal effect of group at follow-up divided by the standard deviation of week 1 adherence scores. Hypothesis 2a: Veterans receiving the behavioral sleep treatment will report at least moderate agreement with items on the Feasibility and Acceptability Questionnaire. Analyses: Descriptive statistics will be calculated for each item of the Feasibility and Acceptability questionnaire, provided in the Appendix. The mean response to each item will be the primary metric for evaluation of this hypothesis. A mean in the range of 4.0 to

**Hypothesis 2b:** There will be lower dropout in the AIR condition compared with the SE condition.

**Analyses:** We will conduct a chi-square analysis to compare dropout in the two conditions (completed all six sessions vs. not).

**Hypothesis 2c:** There will be greater engagement in apnea care in the AIR condition compared with the SE condition.

**Analyses:** We will conduct a chi-square analysis to compare how many Veterans attend their first PAP follow-up appointment with a sleep technician or sleep NP in the two conditions.

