#### **Exploratory Analyses.**

5.0 will be considered acceptable.

**Evaluation of moderators of treatment outcome:** We will evaluate the data for potential moderators of treatment outcomes. This will facilitate adjustments to the protocol prior to a large-scale RCT.

**Analyses:** We will evaluate interactions between subject characteristics and treatment effects to generate hypotheses for informing future work. This exploratory process is necessary because the sample size in the proposed project is insufficiently powered for multiple formal subgroup analyses. In these exploratory analyses, the focus will be on estimated effect sizes rather than statistical significance. These will be calculated based on interaction terms in the models described under Hypothesis 1a above. The primary

moderators of interest are: AHI, concurrent use of sedative-hypnotic medication, baseline PAP self-efficacy (SEMSA), baseline daytime sleepiness (ESS), and baseline sleep quality (PSQI). We will also examine demographic variables and comorbid medical or psychiatric conditions

**Secondary treatment outcomes:** Veterans receiving the behavioral sleep treatment will demonstrate greater increase in sleep efficiency (sleep diary), greater reduction in daytime sleepiness (ESS), greater reduction in PTSD symptom severity (PCL-5), greater improvement in sleep quality (PSQI), and greater improvement in self-efficacy in using PAP (SEMSA) compared with control at post-treatment and follow-up assessment.

**Analyses:** SEF will be the primary variable of interest derived from sleep diaries. The ESS is administered at pre-treatment, sessions 1-6, and post-treatment. The PCL-5, SEMSA, and PSQI are completed at baseline and post-treatment. Separate linear mixed models as described for primary hypotheses 1a and 1b will be estimated for each measure, with each secondary outcome hypothesis tested by the significance of the group difference in baseline-adjusted marginal mean scores post-treatment. Standardized effect sizes will be calculated as the marginal post-treatment group differences divided by pre-treatment standard deviations.

**Evaluation of global treatment satisfaction:** We will examine CSQ-8 total scores for evidence of treatment satisfaction. We will evaluate the data for group differences in treatment satisfaction.

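### Randomization is stratified by therapist but the full-sample outcome models leave therapist out, so reported standard errors may be slightly too large

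*Combined protocol and SAP*

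**What the plan says.** Under Data Collection Procedures, the randomization paragraph describes 1:1 allocation to AIR or SE in randomly permuted blocks of 4 and 6, and adds: "Each therapist will have his or her own randomization list". Each list covers both arms, so each therapist is expected to treat Veterans in both.

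The Statistical Analysis Plan then sets the adjustment policy: "Primary analyses will be unadjusted intent-to-treat analyses, with all subjects randomized to a treatment condition included". Further covariates enter by one route only: "Demographic and other baseline variables that show large group imbalances despite randomization will likewise be entered as covariates in a secondary sensitivity analysis".

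The models are:

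- **WHOQOL-BREF and FOSQ-10 (Hypothesis 1a):** "subjects entered as a random effect and treatment group and time entered as fixed effects", plus the pre-treatment score. The test is visit-specific: "The hypothesis will be tested by the significance of the group differences in baseline-adjusted post-treatment scores".
- **ISI (Hypothesis 1b):** "subjects entered as a random effect and treatment group entered as a fixed effect", plus the pre-treatment score and time.
- **PAP use (Hypothesis 1b):** the ISI model is reused. Of the outcome it says: "This will be measured starting at session 1 and will continue through post-treatment".
- **Secondary outcomes (Exploratory Analyses):** "Separate linear mixed models as described for primary hypotheses 1a and 1b will be estimated for each measure".

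None of these names therapist, and the plan gives no reason for leaving it out.

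**The concern.** Blocking within therapist makes the two arms nearly equal in each caseload, so differences between therapists largely cancel out of the treatment comparison. A model without therapist does not know this. It leaves those differences in the residual and reports a standard error for a less well balanced design than the one used. The imbalance rule does not help, because the blocking that creates the issue also keeps therapist balanced.

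At stake is the reported width of intervals for the primary outcome and the other full-sample outcomes, in a pilot of 80 meant to inform a larger trial. Therapist differences are plausible: AIR is six one-hour sessions that include motivational interviewing and work on barriers to PAP use. The documents give no estimate of their size.

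**Working it through.** **Inputs from the documents.** 40 Veterans per arm (N = 80), 1:1 allocation, blocks of 4 and 6, and one list per therapist. There is no stated power, effect size, standard deviation, alpha or number of therapists, so there is no planned figure to reproduce.

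**Assumptions.** k therapists with equal caseloads; a share r of the baseline-adjusted outcome variance lies between therapists; total adjusted variance 1; a common treatment effect; two-sided alpha of 0.05.

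**Approximation.** With near-equal arms within therapist:

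- true variance of the group difference ≈ (1 − r) × 4/N = (1 − r)/20
- variance reported without therapist ≈ [(1 − r) + r(k − 1)/k]/20
- ratio of standard errors, without / with therapist ≈ √{1 + r(k − 1)/[k(1 − r)]}

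**Example, k = 4 and r = 0.10.** True spread √(0.90/20) = 0.212. Reported standard error √(0.975/20) = 0.221. Ratio √(1 + 0.075/0.90) = 1.041. The effective critical value is 1.96 × 1.041 = 2.04, a type I error of about 4.1%.

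Simulation of this case (6,000 trials, blocks of 4 and 6 within therapist, complete data) gave:

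- true spread 0.2115 without therapist and 0.2110 with it
- mean reported standard error 0.2202 without and 0.2117 with
- type I error 4.1% without and 4.9% with

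The estimate is almost unchanged; what moves is its reported standard error.

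**Range.** The approximation is set against simulation of the post-treatment score on group and pre-treatment score (6,000 runs, complete data).

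| Share r | k = 2, formula | k = 2, simulated | k = 4, formula | k = 4, simulated |
|---|---|---|---|---|
| 0% | 1.000 | 1.000 | 1.000 | 0.999 |
| 2% | 1.005 | 1.005 | 1.008 | 1.007 |
| 5% | 1.013 | 1.013 | 1.020 | 1.018 |
| 10% | 1.027 | 1.027 | 1.041 | 1.041 |
| 15% | 1.043 | 1.044 | 1.064 | 1.063 |

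With a random subject intercept, four occasions and a group-by-time term, the post-treatment contrast gave 1.013-1.043 (2 therapists) and 1.019-1.066 (4) at 5-15%. With 25% of outcomes lost at random, the overstatement is again about 1-6%.

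**Baseline absorption.** If therapists differ only because their caseloads differ stably before and after treatment (5-15% of variance, assumed pre-post correlation 0.6), the pre-treatment score removes most of it. The overstatement is then 0.3-1.2%.

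**PAP use.** The documents are unclear on whether a pre-treatment score exists. Measurement starts at session 1, yet the plan reuses a model with a pre-treatment covariate and refers to a pre-treatment standard deviation. If there is none, nothing is absorbed, and at 5-15% of total variance the overstatement is 1.3-4.1% (2 therapists) or 2.0-6.4% (4).

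**Power.** For an assumed difference of 0.6 SD, power without and with therapist is 76.3% and 76.8% (2 therapists, 5%), a gain of 0.5 points, and 77.3% and 80.9% (4 therapists, 15%), a gain of 3.6 points.

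**The case against.** The planned analysis is valid. It is unbiased and, with a common effect, errs on the conservative side. The documents state no power target that could be breached, every size above is assumed, and the low cases are under 1%. The sponsor also chose unadjusted primary analyses openly. All of this stands, and it is why the point is minor. It does not explain why a factor built into the randomization is absent from the analysis.

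Two objections bear on the fix:

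- **Dropout.** The plan reports past experience of dropout soon after randomization, and losing outcomes disturbs the balance within therapist. With 25% random loss and no therapist differences, adding therapist widens the interval by about 1.0% for 4 therapists and 2.4% for 8. With 4 therapists and 2% of variance, the gain vanishes at 20-30% loss (interval ratio, with / without, 1.000 to 1.005). At 5-10% of variance, a gain of about 1-3% remains.
- **A treatment effect that varies by therapist.** If inference is meant to reach beyond these therapists, the direction reverses. With an assumed between-therapist SD of 0.2-0.3 in the effect, the model standard error is 0.73-0.97 of the true spread without therapist and 0.70-0.91 with it. Type I error goes from 5.7-15.0% to 7.1-16.8%. A therapist main effect does not repair this and makes it slightly worse.

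A reader might also infer a larger problem from the Hypothesis 1a model, which lists group and time but no interaction, by treating the effect as an average over the four visits. The plan does not support that: it tests the post-treatment difference and, separately, the follow-up difference, so the contrasts are visit-specific.

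**Conclusion.** The mismatch is real and its consequence is small and conditional. If therapists differ after baseline adjustment and the treatment effect is common across them, the reported standard error in the full-sample models is too large by about 1-6% (2 to 4 therapists, 5-15% of adjusted variance), by under 1% at 2% of variance, and not at all if they do not differ. The number of therapists and the variance share are assumptions.

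A reader might infer bias, inflated type I error or a noisier estimate. None follows under these conditions: the true spread barely moves and the test is mildly conservative. Nor can it be stated as fact that PAP use lacks a baseline score, since the plan points both ways.

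No defect is claimed for the actigraphy models, the CAPS group-by-time test or the two chi-square tests. Actigraphy is worn by a subset only. In an assumed random subset of 30 with 4 therapists, adding therapist would change interval width by a factor of 1.044 at 0% of variance and 0.982 at 15%, so it could as easily cost as help.

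Severity: minor; a cheap improvement.

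**What to change.** Pre-specify therapist as a fixed effect in the full-sample models for WHOQOL-BREF, FOSQ-10, ISI, PAP use and the secondary outcomes, or as a random intercept if there are many therapists. In the Statistical Analysis Plan, replace the description of the primary analyses as unadjusted with a statement that they are adjusted only for the pre-treatment score, where available, and for the randomization stratum (therapist). That wording would also fit the pre-treatment covariate that the models already contain. Say whether a pre-treatment PAP score exists. Leave the actigraphy, CAPS group-by-time and chi-square analyses as planned. Report treatment effects by therapist descriptively, since a main effect does not address variation in the effect.

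The cost is a few lines of text, no new data, and one degree of freedom per additional therapist. If therapists do not differ, the interval widens by up to about 0.2% with complete data and about 1% with 25% outcome loss for 2 to 4 therapists (about 2.4% for 8). The other cost is the one described above: if the effect varies by therapist and wider inference is intended, a standard error that is already too small becomes slightly smaller. If the sponsor prefers to omit therapist, the plan should give the reason.

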Assessment appointment. In addition, at weeks 1, 3 and 5, the Veteran will complete the primary and secondary functioning outcome measures (WHOQOL-BREF and FOSQ-10.) \*Completion of ISI and ESS, sleep diary data, and PAP adherence are part of routine care and will also be used for research purposes. The additional WHOQOL-BREF AND FOSQ-10 at weeks 1, 3 and 5 are for research purposes.

**Post-Treatment Assessment.** One week following his or her final treatment appointment, the Veteran will attend the post-treatment assessment appointment via phone or video. He or she will turn in the sleep diary with data from the preceding week. He or she will turn in the actigraphy device. The Veteran will complete post-treatment questionnaires. A trained, blinded clinical interviewer will repeat the CAPS-5 interview (current symptoms only) and SCID-5 (insomnia portion only) and inquire about medication changes. The Veteran will complete a brief feedback interview about their treatment experience with study staff. The Veteran's PAP adherence data will be downloaded or provided verbally. \*This is for research purposes.

**3-Month Follow-Up Assessment.** Veterans will complete the 3-month follow-up questionnaires. PAP adherence data will be downloaded or provided verbally. If the Veteran's PAP device does not have a functional modem, the study team will arrange for the Veteran to provide their SD card for data download. The data will be uploaded to the appropriate clinical data monitoring system and the SD card will be returned to the Veteran. Veterans' charts will be checked to track PAP follow-up appointment attendance, if applicable. Veterans will be sent a sleep diary to complete the week prior to this appointment and will submit it at this appointment. \*This is for research purposes. However, review of PAP adherence data at 3-month follow-up is also part of routine care in the Sleep Clinic.

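### In-treatment ISI and ESS are collected only at attended sessions, with no route for Veterans who stop; the intent-to-treat estimate is at risk to the extent that stoppers also miss post-treatment

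*Combined protocol and SAP*

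**What the plan says.** Under Data Collection Procedures, the Weekly assessment paragraph ties two scales to the session: "At the start of each treatment appointment, the Veteran will complete two self-report questionnaires assessing sleep (ISI and ESS". The analysis plan repeats this for the ISI (Hypothesis 1b, Analyses for insomnia): "The ISI is administered several times over the course of treatment: pre-treatment, sessions 1-6, and post-treatment". The Secondary treatment outcomes text gives the ESS the same schedule. Neither place lists a follow-up value for these two scales.

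The same Weekly assessment paragraph adds the quality-of-life and functioning scales: "at weeks 1, 3 and 5, the Veteran will complete the primary and secondary functioning outcome measures (WHOQOL-BREF and FOSQ-10". These are dated by week and no collection route is given, so a link to attendance is inferred from placement only.

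The post-treatment sleep diary is requested at a session: "At his or her final treatment appointment, the Veteran will be asked to complete a sleep diary to submit at the Post-Treatment". The post-treatment visit is separate and remote, but is dated from the last session: "One week following his or her final treatment appointment, the Veteran will attend the post-treatment assessment appointment via phone or video".

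The analysis plan states: "Primary analyses will be unadjusted intent-to-treat analyses, with all subjects randomized to a treatment condition included". It relies on linear mixed models under missing at random for data lost to dropout, and Hypothesis 2b defines dropout as not completing all six sessions. Leaving treatment and leaving the study are not separated.

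A remote route already exists for the baseline diary: "Research staff will email the Veteran a link to enter sleep diary data via Qualtrics".

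**The concern.** An intent-to-treat comparison needs outcomes from Veterans who stop therapy as well as from those who continue. Where values exist only while a Veteran attends, the mixed model fills the gap from the trajectories of Veterans who stayed in the same arm. If AIR works, part of its benefit is then credited to Veterans who left it.

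The ISI is the outcome most exposed. Its post-treatment difference is a marginal mean from a model fitted to all sessions, with time possibly entered as a fitted curve, so in-treatment values shape the estimate. The 3-month visit cannot make up the loss, because the plan lists no follow-up value for ISI or ESS.

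Stopping is a live issue in this trial. The Dropout paragraph says that in the team's earlier trials most dropout came right after randomization. A Veteran who attends no session has no in-treatment ISI or ESS and no last session from which to date the post-treatment visit. Values that were never requested cannot be recovered at analysis.

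**Working it through.** **Inputs from the documents.** 40 per arm, 1:1 allocation; ISI at pre-treatment, sessions 1-6 and post-treatment (seven occasions after baseline); test at post-treatment. The documents give no dropout rate, effect size or SD, so there is no planned figure to reproduce.

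**Assumed inputs.** ISI effect of 0.8 SD at post-treatment among completers, growing linearly over the seven occasions; equal stopping in both arms, 20% in the main case; stoppers split evenly between 0 and 1 session and keeping only the effect reached; random intercept and slope; baseline score as covariate; linear group-by-time model read at post-treatment.

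**True intent-to-treat effect.** Effect kept by a stopper: the average of 0 and 0.8/7 = 0.114, which is 0.057 SD. At 20% stopping: 0.80 × 0.8 + 0.20 × 0.057 = 0.64 + 0.011 = 0.65 SD. At 30%: 0.70 × 0.8 + 0.30 × 0.057 = 0.58 SD.

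**Simulated estimates, large samples, 20% stopping (true 0.65 SD).**

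| Stoppers seen at post-treatment | Session-tied | Excess | With weekly links answered by 70% of stoppers | Excess |
|---|---|---|---|---|
| None | 0.81 | 0.16 (25%) | 0.71 | 0.06 (9%) |
| Half | 0.74 | 0.09 (14%) | 0.69 | 0.04 (6%) |
| All | 0.67 | 0.02 (3%) | 0.66 | 0.01 (2%) |

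Excess is the estimate minus 0.65; the percentage is that divided by 0.65. Separate runs with other assumed variance components agreed within about 0.01 to 0.03. The session-tied value with all stoppers seen ranged from 0.67 to 0.70. That remainder comes mainly from forcing a straight line, and a quadratic curve left no meaningful bias in that case.

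**Range.**
- At 30% stopping (true 0.58), session-tied against weekly links gives 0.80 against 0.64 with no stopper seen at post-treatment, 0.69 against 0.61 with half, and 0.63 against 0.60 with all.
- If stopping comes later, after 1 to 4 sessions, and no stopper is seen at post-treatment, the overstatement at 20% stopping is 17%, falling to 7% with links.

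**Precision.** At 20% stopping with none seen at post-treatment, the standard error with 40 per arm fell from 0.177 to 0.164 in one run (0.013/0.177 = 7%) and from 0.185 to 0.171 in another (0.014/0.185 = 8%). Another set of variance components gave about 6%. The gain is smaller when more stoppers are seen.

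**Primary outcome (WHOQOL-BREF, categorical time, assumed 0.5 SD, 20% stopping, no effect kept after stopping).** The true intent-to-treat effect is 0.80 × 0.5 = 0.40 SD. If stoppers give nothing after stopping, post-treatment and follow-up included, the model returns 0.51. If only in-treatment values are lost, it returns 0.39. Adding remote collection at weeks 3 and 5 alone moves the bias from about 0.10 to 0.08 SD; it falls to about 0.02 SD only when post-treatment is also answered.

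**The case against.** The strongest reply is that the hypotheses are tested at post-treatment, and post-treatment is not a therapy session. It is a separate phone or video visit with its own questionnaires and a blinded interviewer, followed by a separate 3-month assessment, and neither is made conditional on attendance. A reader might infer from the Weekly assessment paragraph that a Veteran who stops sessions gives no further outcome data, and that the intent-to-treat estimate therefore becomes the effect had everyone kept attending. The documents do not support that. They are silent on whether stoppers are assessed at post-treatment, and the full shift appears only if that visit is lost as well. This part of the reply stands, and it makes retention at post-treatment the larger lever.

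Two further points also stand. The comparison in which no stopper attends post-treatment but 70% answer links is favourable to links, and neither rate comes from the documents. WHOQOL-BREF and FOSQ-10 are scheduled by week, so their dependence on attendance is an inference.

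The reply does not remove the point. Nothing assures the post-treatment visit for stoppers, and its date is undefined for a Veteran with no session. With half of the stoppers seen, session-tied ISI collection still overstates the effect by 0.09 SD in the example, against 0.04 SD with links.

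**Conclusion.** The point holds in a limited form. The documents state a collection rule for ISI and ESS that yields nothing during treatment from a Veteran who is not attending, and they describe no alternative. The consequence depends on post-treatment retention of stoppers, which they leave open. Under the stated assumptions at 20% stopping, the ISI overstatement runs from about 0.16 SD (none seen at post-treatment) through 0.09 (half) to 0.02 (all; up to 0.05 in other runs). The last is small beside a standard error of 0.16 to 0.19 with 40 per arm. ESS has the same schedule and would behave similarly. For the primary WHOQOL-BREF outcome, collecting weeks 3 and 5 remotely helps little unless post-treatment is answered too.

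The direction of the bias rests on stoppers losing benefit after they leave. Its size rests on the assumed effect, stopping rate, timing of stopping and response rates. The change is worth making because it is inexpensive and serves the intent-to-treat comparison that the plan promises.

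**What to change.** In the Weekly assessment paragraph, send ISI and ESS weekly, and WHOQOL-BREF and FOSQ-10 at weeks 1, 3 and 5, to every randomized Veteran by the existing Qualtrics link. Use study weeks, counted for example from the scheduled date of session 1, and send the link whether or not the session is attended or treatment has stopped. Keep completion at the start of the session, or a Research Assistant call, as back-up.

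In the Post-Treatment Assessment paragraph, state that every randomized Veteran is contacted regardless of attendance, and request the post-treatment diary on the same study-week clock so that the visit has a date for a Veteran with no session.

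In the analysis plan, index time by study week, state that values collected after stopping enter the intent-to-treat analysis, and record stopping treatment separately from leaving the study.

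The cost is wording in both parts of the document, some set-up in a system already in use, and Research Assistant reminders. The downside is a few more contacts with Veterans who have stopped, and possibly slightly smaller estimated effects.
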